- Interim medical history, including an assessment for new medical conditions, stability of chronic diseases, and symptoms suggestive of PIMMCs, will be obtained by interview of subjects and any changes since the previous clinic visit or contact will be noted.
- Memory aid information will be reviewed with subjects.
- All concomitant medications (including solicitation for receipt of any non-study influenza vaccines, including those that are experimental, what type (inactivated or live attenuated), what subtype (e.g., A/H3, A/H5, A/H9) and approximate date of vaccination will be

recorded on the appropriate DCF, if known and not previously collected) will be recorded on the appropriate DCF.

- All AE/SAEs will be recorded on the appropriate DCF.
- A targeted physical examination, including an assessment for signs suggestive of PIMMCs, may be performed, if indicated based on review of interim medical history, by a study clinician licensed to make medical diagnoses and listed on the Form FDA 1572 as the site principal investigator or sub-investigator.
- The H7N9 and IIV4 vaccination sites will be examined.
- Approximately 10 mL of venous blood will be collected for safety labs, WBC, Hgb, PLT, ALT, T. Bili, Cr, and performed by the central (clinical) laboratory.
- Approximately 10 mL of venous blood will be collected for future research from subjects who consent, either by signing an informed consent form that includes collection of future use samples as a condition of study participation or by indicating that they opt in to sample collection for future use if the informed consent form allows the option to choose that option.

8.2.3 Visit 04, Day 22, Dose 2, Clinic Visit (Window: 21 (+7) days post Dose 1)

- Eligibility criteria will be reviewed with subjects prior to the vaccination to ensure continued eligibility.
- For a subject to receive the vaccination, refer to [section 5.2.3](#) for subsequent dose eligibility criteria.
- Interim medical history, including an assessment for new medical conditions stability of chronic diseases and symptoms suggestive of PIMMCs, will be obtained by interview of subjects prior to the vaccination and any changes since the previous clinic visit or contact will be noted.

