- Interim medical history, including an assessment for new medical conditions, stability of chronic diseases, and symptoms suggestive of PIMMCs, will be obtained by interview of subjects and any changes since the previous clinic visit or contact will be noted.
- Memory aid information will be reviewed with subjects.
- All concomitant medications (including solicitation for receipt of any non-study influenza vaccines, including those that are experimental, what type (inactivated or live attenuated), what subtype (e.g., A/H3, A/H5, A/H9) and approximate date of vaccination will be recorded on the appropriate DCF, if known and not previously collected) will be recorded on the appropriate DCF.
- All AE/SAEs will be recorded on the appropriate DCF. Note: for subjects who discontinued from the receipt of Dose 3, AEs will be limited to SAEs and MAAEs, including NOCMCs and PIMMCs.

- A targeted physical examination, including an assessment for signs suggestive of PIMMCs, may be performed, if indicated based on review of interim medical history, by a study clinician licensed to make medical diagnoses and listed on the Form FDA 1572 as the site principal investigator or sub-investigator.
- The third vaccination site will be examined.
- Approximately 10 mL of venous blood will be collected for safety labs, WBC, Hgb, PLT, ALT, T. Bili, Cr, and performed by the central (clinical) laboratory.
- Approximately 10 mL of venous blood will be collected for future research from subjects who consent, either by signing an informed consent form that includes collection of future use samples as a condition of study participation or by indicating that they opt in to sample collection for future use if the informed consent form allows the option to choose that option.

8.3.9 Visit 10, Day 64, Safety Follow-up, Clinic Visit (Window: 21 (+7) days post Dose 3)

- Interim medical history, including an assessment for new medical conditions, stability of chronic diseases, and symptoms suggestive of PIMMCs, will be obtained by interview of subjects and any changes since the previous clinic visit or contact will be noted.

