8.5 Early Termination Visit (if needed)

The following activities will be performed at the early termination visit on subjects who withdraw, are withdrawn, or terminated from this trial:

- Interim medical history, including an assessment for new medical conditions and symptoms suggestive of PIMMCs, will be obtained by interview of subjects and any changes since the previous clinic visit or contact will be noted.

- Memory aid information will be reviewed with subjects (if within 7 days after the last study vaccination).
- All concomitant medications will be recorded on the appropriate DCF (if within 21 days after the last study vaccination). Receipt of any non-study influenza vaccine, including those that are experimental, what type (inactivated or live attenuated), what subtype (e.g., A/H3, A/H5, A/H9) and approximate date of vaccination will be recorded on the appropriate DCF, if known and not previously collected, will be recorded if within 180 days after the last vaccination.
- All AE/SAEs will be recorded on the appropriate DCF. AEs will be limited to SAEs and MAAEs, including NOCMCs and PIMMCs, that have occurred since the previous clinic visit or contact will be solicited (if after 21 days after the last vaccination).
- Vital signs, including oral temperature, pulse, and blood pressure, may be obtained if indicated. Subjects must not eat or drink anything hot or cold, or smoke within 10 minutes prior to taking oral temperature.
- A targeted physical examination, including an assessment for signs suggestive of PIMMCs, may be performed, if indicated based on review of interim medical history, by a study clinician licensed to make medical diagnoses and listed on the Form FDA 1572 as the site principal investigator or sub-investigator.
- The study vaccination site(s) will be examined (if within 7 days after the last vaccination).
- Post-administration reactogenicity assessments will be performed (if within 7 days after the last vaccination).
- Approximately 10 mL of venous blood will be collected for WBC, Hgb, PLT, ALT, T. Bili, Cr, and performed by the central (clinical) laboratory (if within 7 days after the last vaccination).
- Approximately 10 mL of venous blood will be collected for serum antibody assays (if within 21 days after the last vaccination).
- Approximately 10 mL of venous blood will be collected for future research from subjects who consent (if within 21 days after the last vaccination).

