Vital Signs\$ (Oral Temperature%, Pulse, and BP)						X (may be obtained if indicated)	X (may be obtained if indicated)
Physical Examination ^³	{X}	{X}	{X}	{X}		{X}	{X}
Venous Blood Collection for Clinical Safety Laboratory Evaluations [~]						X (if within 7 days after the last study vaccination)	X (if indicated)
Venous Blood Collection for Immunogenicity Assays	X		X	X		X(if within 21 days after last study vaccination)	X(if within 21 days after last study vaccination)
Serum Sample Collected for Future Research ^⁴	X	X	X	X		X(if within 21 days after last study vaccination)	X(if within 21 days after last study vaccination)

Safety Follow-up Phone Call					X		
Examine Study Vaccination Site						X (if within 7 days after last study vaccination)	X (if within 7 days after last study vaccination)
Post-Administration Reactogenicity Assessments						X (if within 7 days after last study vaccination)	X (if within 7 days after last study vaccination)
Review Memory Aid						X (if within 7 days after last study vaccination)	X (if within 7 days after last study vaccination)
AE/SAE Assessment	X	X	X	X	X	X&	X&

^a Complete medical history will be obtained by interview of subjects at screening (optional) or on Day 1 prior to the first study vaccination and interim medical history will be obtained by interview of subjects at follow-up visits after Dose 1

^c Receipt of non-study influenza vaccines will be solicited through approximately 180 days after the last study vaccination, and reported in the eCRF.

^s Vital signs assessed on Day 1 prior to the first study vaccination will be considered as baseline.

[%] Subjects must not eat or drink anything hot or cold, or smoke within 10 minutes prior to taking oral temperature.

^{} Targeted physical examination if indicated based on review of interim medical history

[~] Includes WBC, Hgb, PLT, ALT, T. Bili, Cr.

[¶] Subjects who do not receive the third study vaccination will continue with follow-up safety assessments (may be conducted by phone call) rather than in person continuing through approximately 12 months after their first study vaccination. These subjects will also be encouraged to provide a venous blood sample for immunogenicity assays at approximately 21 and 180 days after their first study vaccination.

⁴ For subjects who have consented to collection of serum for future use.

Study Schedule, Group 2: Vaccination Period

Study Visit Number	V00	V01	V02	V03	V04 [¶]	V05	V06	V07 [¶]	V08

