
[@] Complete medical history will be obtained by interview of subjects at screening (optional) or on Day 1 prior to study vaccination and interim medical history will be obtained by interview of subjects at follow-up visits after the study vaccination.

[¤] Receipt of non-study influenza vaccines will be solicited through approximately 180 days after the study vaccination, and reported in the eCRF.

^{*} Not required if done at the optional screening visit.

[√] All current medications and medications taken within 60 days prior to signing the ICF.

[§] Vital signs assessed on Day 1 prior to the study vaccination will be considered as baseline.

[%] Subjects must not eat or drink anything hot or cold, or smoke within 10 minutes prior to taking oral temperature.

^³ At the screening (or baseline if not done at screening) visit, a physical examination will be performed on all subjects to include the following organs and organ systems: skin, head and neck, lungs, heart, liver, spleen, extremities, lymph nodes, and nervous system.

^{} Targeted physical examination if indicated based on review of interim medical history.

[^] May be performed on all women of childbearing potential at screening (optional) and will be performed within 24 hours prior to study vaccination and results must be negative.

[#] To be performed locally by the site. The ESR value must be confirmed as <30 mm/hr prior to randomization and study vaccination.

[~] Includes WBC, Hgb, PLT, ALT, T. Bili, Cr.

^⁴ For subjects who have consented to collection of serum for future use.

[&] Inclusive of reactogenicity assessments performed on the day of vaccination through 7 days after study vaccination.

Early Termination and Unscheduled Visits, Group 3

Study Visit Number	Early Termination (if needed)	Unscheduled (if needed)
Study Day post dose		
Medical History [@]	X	X (if indicated)

Concomitant Medications	X (if within 21 days after last study vaccination and receipt of any non-study influenza vaccine will be recorded if within 180 days after the 2nd study vaccination)	X (if within 21 days after last study vaccination and receipt of any non-study influenza vaccine will be recorded if within 180 days after the 2nd study)
Vital Signs (Oral Temperature ^{%,} , Pulse, and BP)	X (may be obtained if indicated)	X (may be obtained if indicated)
Physical Examination ³	{X}	{X}

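### Early Termination cut-offs end on the first day of the matching visit windows, so a withdrawing subject can leave with in-window data that no rule asks the site to collect

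*Protocol*

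**What the plan says.** Protocol section 8.5 sets time limits on what is done at the Early Termination (ET) visit.

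- **Antibody sample:** "Approximately 10 mL of venous blood will be collected for serum antibody assays (if within 21 days after the last vaccination".
- **Memory aid:** "Memory aid information will be reviewed with subjects (if within 7 days after the last study vaccination". Site examination and reactogenicity assessment carry the same 7-day limit.
- **Safety labs:** "performed by the central (clinical) laboratory (if within 7 days after the last vaccination".
- **Adverse events (AEs):** the visit is restricted to serious and medically attended events "that have occurred since the previous clinic visit or contact will be solicited (if after 21 days after the last vaccination".

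The ET columns of Appendix A repeat the limits on blood, site examination, reactogenicity and memory aid, for example "X(if within 21 days after last study vaccination" for the antibody row. So do SAP Tables 3, 5 and 7. The AE restriction stands in the text of 8.5 and 8.6, not in those columns.

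The scheduled visits that collect the same data have windows that open on the nominal day and run later. The Group 1 Day 22 visit (8.2.3) has "Window: 21 (+7) days post Dose 1" and the Group 2 Day 64 visit (8.3.9) has "Window: 21 (+7) days post Dose 3". The Group 1 Day 43 visit (8.2.6) and the Group 3 Day 22 visit (8.4.3) are built the same way. The 7-day visits are 7 (+2).

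For non-study influenza vaccines, the ET columns of Appendix A state that "receipt of any non-study influenza vaccine will be recorded if within 180 days after the 2nd study vaccination". Sections 8.5 and 6.6 count 180 days from the last vaccination.

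**The concern.** Each ET limit ends on the day the matching window opens. The ET visit therefore asks for an item before its window and on its first day, and stops asking for the rest of the window. For the 21-day antibody sample, those later days are when the result is fully in window for a primary endpoint.

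Any loss falls only on subjects who withdraw, and it cannot be recovered once they have left. Missing values are not imputed (Protocol 11.6.4, SAP 6.5). The primary analysis population is mITT (SAP 8.1), and membership needs at least one valid post-vaccination result (SAP 6.3.2). A subject who terminates on days 22-28 after Dose 1 without the Day 22 draw leaves that population altogether. One who terminates on days 22-28 after the second H7N9 dose without the Day 43 or Day 64 draw stays in mITT if the Day 22 sample was taken, but has no primary H7N9 titre.

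The AE restriction is a related problem. It depends on the date of the visit, whereas the collection period in sections 9.1 and 9.3 depends on when the event occurs.

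**Working it through.** **1. The plan's own sample-size figures.** Section 11.4.2 enrols 60, 60 and 30 and allows up to 15% loss. 60 × 0.85 = 51, at least 50; 30 × 0.85 = 25.5, at least 25. Exact enumeration of the two-sided likelihood ratio test at alpha 0.05 gives power 0.80-0.81 at the Table 5 differences (50 per group) and 0.79-0.82 at the Table 6 differences (75 against 50). These figures reproduce, and nothing in this point disputes them.

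**2. ET limit against scheduled window, in days after the relevant dose.**

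| Item | ET limit (8.5) | Scheduled window | Window days covered |
|---|---|---|---|
| 21-day antibody sample | up to 21 | 21 to 28 | 1 of 8 |
| Safety labs, site examination | up to 7 | 7 to 9 | 1 of 3 |
| Memory aid review | up to 7 | 7 to 9 | 1 of 3 |
| 180-day antibody sample | nothing after 21 | 166 to 194 | 0 of 29 |

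The last row is 180 − 14 = 166 to 180 + 14 = 194, which is 29 days. Section 8.3.2 gives the Group 2 Day 8 window as 7 (±2), while Table 2b and Appendix A give +2; the table uses +2.

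**3. What is missed, by day of an ET visit made before the scheduled visit.**

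- Up to day 7: nothing listed in 8.5 is cut off.
- Days 8-9: the antibody sample and all AEs are still collected. Memory aid review, site examination and safety labs are not specified.
- Days 10-21: the antibody sample and all AEs are still collected. The 7-day window has closed, but a memory aid not yet reviewed stays unreviewed.
- Days 22-28: no antibody sample is specified and AEs are restricted. The 7-day items were due earlier.

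**4. Would a day 22-28 sample count?** Yes, absent any other exclusion. mITT has no visit-window exclusion. Per-protocol drops only visits more than one day out of window (SAP 6.3.3), and days 22-28 are inside it.

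**5. AEs.** Take a Group 1 subject seen 7 days after Dose 2 and next seen 25 days after it. At scheduled Visit 07 (8.2.6) all AEs are recorded. At an ET visit that same day only serious and medically attended events are. A non-serious event with onset on day 15, not yet reported, lies inside the collection period in 9.1 and 9.3 but is not sought.

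**6. Non-study influenza vaccine cut-off.** Table 1 defines the Group 1 Day 1 dose as the first and second study vaccinations.

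- Group 1: 180 days from the second vaccination is Day 181; from the last (Day 22) it is Day 202.
- Group 2: Day 202 from the second (Day 22) against Day 223 from the last (Day 43).
- Group 3: there is no second vaccination, so the cut-off is undefined.

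**7. Fallbacks.** The Unscheduled Visit (8.6) repeats the antibody, site-examination, memory-aid and AE limits; only its safety lab is open, if indicated. Section 5.2.4 encourages samples at about 21 and 180 days from subjects who miss a dose and remain in follow-up. The opening of section 8 sends discontinued subjects who remain on study to the Manual of Procedures. Neither covers a subject who terminates.

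**The case against.** The strongest reply is that a subject who attends on days 21-28 is attending the scheduled visit, which has its own draw. A reader might infer that someone who comes for a deferred Dose 2 on Day 24, declines it and leaves the trial loses the primary IIV4 sample. The documents do not support that. The subject is at Visit 04, inside its window, and 8.2.3 lists the draw before the injection; only vital signs are waived for subjects discontinued from the dose. No text says that ET cancels a scheduled visit then due, and 8.5 lists what will be done without forbidding more. What stands is narrower: if the visit is handled only as ET, the supplied text specifies no draw.

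A reader might also infer that one subject loses everything together, or that early ET samples are useless. Step 3 shows that the losses depend on the day. The out-of-window rule is per-protocol only, and it tolerates one day, so day 20 counts there too. Section 7.2.2 says early withdrawers' available sera will be assayed.

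On AEs, 5.2.4 follows events ongoing at withdrawal and 9.2.5 requires observed or reported AEs to be recorded. Known events are therefore kept, and reactions already noted at the Day 4 call are not lost. Neither provision asks about events not yet reported. The 180-day titres are exploratory. The non-study vaccine cut-off is a separate inconsistency, but it sits in the same columns and is a plain contradiction.

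**Conclusion.** The mismatch is real and should be corrected. The ET limits end on the first day of the matching windows. For a visit handled only as ET before the scheduled visit was done, this leaves no antibody draw specified on 7 of 8 window days, and no safety labs, site examination or memory aid review on 2 of 3. The AE restriction conflicts with the collection period in 9.1 and 9.3, and Appendix A conflicts with 8.5 and 6.6 on the non-study vaccine cut-off.

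The number affected is unknown, probably small and possibly zero. It is tempting to take 15% of the 120 subjects in Groups 1-2 (18) and assign a share of them to days 22-28. The documents do not support this. Section 11.4.2 builds its 15% from missed doses, loss to follow-up and protocol deviations together; subjects lost to follow-up have no ET visit, and many of the others may stay in the trial. The arithmetic ceiling is 0.15 × 60 = 9 per group, reached only if the whole allowance terminated in those days without the scheduled visit.

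Planned sample size and power do not change, because the plan already rests on 50, 50 and 25. The conclusion assumes that the Manual of Procedures, which was not supplied, does not already extend the ET limits.

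**What to change.** Amend section 8.5, the ET columns of Appendix A and SAP Tables 3, 5 and 7.

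- **Windowed items:** keep the current earlier collection, and add that a scheduled item not yet done is collected at ET if the visit falls inside its existing window. That is days 21-28 and 180 ± 14 for antibody, and days 7-9 for safety labs and site examination.
- **Memory aid:** review any 7-day memory aid not yet reviewed, whatever the visit day.
- **AEs:** record all non-serious AEs with onset within 21 days of the last vaccination, whatever the visit date.
- **Non-study influenza vaccine:** count from the last vaccination, as in 8.5 and 6.6.

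Make the matching change in 8.6, and settle whether the Group 2 Day 8 window is ±2 or +2.

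The cost is protocol and SAP wording. In a few subjects it adds at most the tubes and memory aid review already planned at the scheduled visit, with no extra visits.

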8.6 Unscheduled Visit (if needed)

Unscheduled visits may occur at any time during this trial. Any of the following activities may be performed:

- Interim medical history, including an assessment for new medical conditions and symptoms suggestive of PIMMCs, will be obtained by interview of subjects and any changes since the previous clinic visit or contact will be noted (if indicated).
- Memory aid information will be reviewed with subjects (if within 7 days after the last vaccination).
- All concomitant medications will be recorded on the appropriate DCF (if within 21 days after the last vaccination). Receipt of any non-study influenza vaccine, including those that are experimental, what type (inactivated or live attenuated), what subtype (e.g., A/H3, A/H5, A/H9) and approximate date of vaccination will be recorded on the appropriate DCF, if known and not previously collected, will be recorded if within 180 days after the last vaccination.
- All AE/SAEs will be recorded on the appropriate DCF. AEs will be limited to SAEs and MAAEs, including NOCMCs and PIMMCs, if after 21 days after the last vaccination.
- Vital signs, including oral temperature, pulse, and blood pressure, may be obtained if indicated. Subjects must not eat or drink anything hot or cold, or smoke within 10 minutes prior to taking oral temperature.
- A targeted physical examination, including an assessment for signs suggestive of PIMMCs, may be performed, if indicated based on review of interim medical history, by a study clinician licensed to make medical diagnoses and listed on the Form FDA 1572 as the site principal investigator or sub-investigator.
- The study vaccination site(s) will be examined (if within 7 days after the last vaccination).
- Post-administration reactogenicity assessments will be performed (if within 7 days after the last vaccination).
- Approximately 10 mL of venous blood will be collected for WBC, Hgb, PLT, ALT, T. Bili, Cr, and performed by the central (clinical) laboratory (if indicated).
- Approximately 10 mL of venous blood will be collected for serum antibody assays (if within 21 days after the last vaccination).

- Approximately 10 mL of venous blood will be collected for future research from subjects who consent (if within 21 days after the last vaccination).

9 ASSESSMENT OF SAFETY

9.1 Specification of Safety Parameters

Safety will be assessed by the frequency and severity of:

1. SAEs occurring from the time of the first study vaccination through approximately 12 months after the last study vaccination.
2. Solicited AEs – reactogenicity events occurring from the time of each study vaccination through 7 days after each study vaccination:
 - a) Injection site reactions including pruritus, ecchymosis, erythema, induration (hardness)/edema (swelling), pain, and tenderness.
 - b) Systemic reactions including fever, feverishness, fatigue, malaise, myalgia, arthralgia, headache, and nausea.
3. Clinical safety laboratory AEs occurring from the time of each study vaccination through approximately 7 days after each study vaccination. Parameters to be evaluated include WBC, Hgb, PLT, ALT, T. Bili, Cr.
4. Unsolicited AEs – non-serious AEs occurring from the time of each study vaccination through approximately 21 days after each study vaccination.
5. MAAEs, including NOCMCs and PIMMCs, occurring from the time of the first study vaccination through approximately 12 months after the last study vaccination.

